11. CASE REPORT FORM COMPLETION

Staff delegated to complete the data entry will be trained to adhere to:

- CRF completion and corrections
- Date format
- Time format and unknown times
- Rounding conventions
- Trial-specific interpretation of data fields
- Entry requirements for concomitant medications (generic or brand names)
- Which forms to complete and when
- What to do in certain scenarios, for example when a patient withdraws from the trial
- Missing/incomplete data
- Reporting SAEs
- Repeat laboratory tests
- Protocol and GCP non-compliances

11.1.1. Electronic data entry at site

Data reported on the eCRF will be consistent with the source data and any discrepancies will be explained. All missing and ambiguous electronic data entry will be queried. Paper worksheets replicating the data to be entered on the eCRF will be provided to sites and may be used to capture data variables.

11.1.2. UK specific CRFs

For the UK specific outcomes, data reported on the CRF and eCRF will be consistent with the source data and any discrepancies will be explained. All missing and ambiguous data will be queried.

In all cases, it remains the responsibility of the site's PI to ensure that the CRFs and patient questionnaires are completed correctly, and that the data are accurate. This will be evidenced by the signature of the site's PI, or delegate(s), on the CRF and eCRF.

11.2. Patient Completed Questionnaires

For the UK specific outcomes, the EQ-5D-5L and WHODAS 2.0 questionnaire will be completed and forms part of the secondary outcomes. Patients randomised into the VITDALIZE UK Trial will be critically ill therefore there will be situations where the patient will be unable to complete the questionnaires. In those scenarios, the patients legal representative will complete them as 'proxy'. If the patient is unable to complete the questionnaires alone, the research staff can provide physical assistance where appropriate. In such circumstances, questions are to be read to the patient verbatim and research staff must not lead responses.

Patients or their legal representative should be encouraged to respond to all questions but can refuse to answer any or all of the questions should they wish.

Patient completed questionnaires will be completed either in clinic/bedside or via telephone dependent on the location of the patient at that visit. If the questionnaires are completed in clinic/bedside, the patient or legal representative should complete the questionnaires. The research staff delegated the task should oversee their completion. Where a questionnaire is returned to the research staff, in person, with some questions unanswered, research staff should clarify with the patient that they have chosen not to respond specifically to the unanswered questions and that they have not simply missed them in error.

Where a questionnaire is completed via telephone, the research team at site are required to read questions from the questionnaire to the patient or legal representative verbatim and must not lead responses. In situations where the patient or legal representative do not answer or refuse to answer a question, the research team at site will move on to the following question.

11.3. **Health Economics Analysis**

The health economics (resource use) questionnaire will be completed via telephone. The research team at site are required to read questions from the questionnaire to the patient or legal representative verbatim and must not lead responses. In situations where the patient or legal representative do not answer or refuse to answer a question, the research team at site will move on to the following question. NHS digital, ONS/HES data will be collected at the end of trial follow-up to collect long term outcomes (survival status).

11.4. Data Management

Data for the VITDALIZE UK Trial will be entered on 2 databases. The main trial outcomes will be collected via the eCRF, the additional UK specific outcomes will be collected on the UK database.

Data entered on the eCRF will be completed by the research staff at site whereas data items for the UK database will be entered by the VITDALIZE UK Trial Office.

Processes will be employed to facilitate the accuracy of the data included in the final report. These processes will be detailed in the VITDALIZE UK Data Management Plan (DMP). For the UK specific database, coding and validation will be agreed between the Trial Manager, Statistician and Analyst Programmer and the trial database will be signed off once the implementation of these has been assured.

Missing and ambiguous data for VITDALIZE UK will be queried using a data clarification system in line with the VITDALIZE UK DMP and will focus on data required for trial outcome analysis and safety reporting. Data entry for VITDALIZE UK will consist of electronic and paper data entry. Data entry for the main trial will consist of remote data capture and entry by the research staff at site; UK specific outcomes will be entered centrally by the VITDALIZE UK Trials team (See Table 4).

11.4.1. Data management for electronic data entry at site

Research staff at site who are delegated the role of CRF completion will enter and submit data on the eCRF. They will be provided with unique log-in usernames and passwords to use the online system. These unique log-in details must not be shared with other staff and in no circumstances should staff at sites access the trial database using another person's login details. The VITDALIZE UK Trial Office will be unable to edit data forms entered by site staff on the eCRF. The system will include data validations to improve data quality (e.g. to prevent nonsensical dates or numerical values). Changes to the data on the system will be documented and attributable, with a reason for the change documented and will be made by the research staff at site.

11.4.2. Data management for paper data entry (UK-specific outcomes only)

UK specific outcomes will be captured using paper CRFs and entered centrally by the VITDALIZE UK Trials Office. The research staff at site will be responsible for sending the paper CRFs to the VITDALIZE UK Trial Office for data entry. Sites will be sent Data Clarification Forms (DCF) requesting missing data or clarification of inconsistencies or discrepancies per the DMP.

VITDALIZE UK is a CTIMP which has been formally risk assessed by BCTU as 'Type A' on the basis that the intervention has a well-established safety profile. Therefore, on-site monitoring will, for the most part, be triggered by poor recruitment or poor data returns. CRFs may be checked against the source data where on-site monitoring is conducted and must be available for verification.

Table 4: Data Entry

eCRF (remote) data entry	Paper CRF data entry			
Baseline – Day 0	Eligibility checklist form			
• Day 5	Informed consent form			
• Day 28	Contact details form			
• Day 90	Questionnaires (EQ-5D-5L; WHODAS 2.0)			
1 Year	Change of status form			
Discharge information	Health economics questionnaire form			
Study discontinuation	SAE form			
Adverse event reporting	Pregnancy form			
SAE form (international)				

11.5. **Data Security**

Every international centre working on the VITDALIZE Trial will have access to the eCRF Clincase (Quadratek, Data Solutions Ltd., Berlin, Germany). Clincase is a validated electronic data capture and clinical data management system which complies fully with the European Union (EU) and Good Manufacturing Practice (GMP) Annex 11 regulations.

Data security for the eCRF is the responsibility of the Medical University of Graz, Austria.

The access to the eCRF is secured by a rights and role system with password aging.

Internet communication with the eCRF uses to the Transport Layer Security (TLS) and includes data back-up and data mirroring.

The security of the UK database system is governed by the policies of the University of Birmingham. The University's Data Protection Policy and the Conditions of Use of Computing and Network Facilities set out the security arrangements under which sensitive data should be processed and stored. All studies at the University of Birmingham have to be registered with Data Protection Officer and data held in accordance with the Data Protection Act. The University will designate a Data Protection Officer upon registration of the trial. BCTU have arrangements in place for the secure storage and processing of the trial data, which comply with the University of Birmingham policies.

The System incorporates the following security countermeasures:

 Physical security measures: restricted access to the building, supervised onsite repairs and storages of back-up tapes/disks are stored in a fire-proof safe.

- Logical measures for access control and privilege management: including restricted accessibility, access-controlled servers, separate storage of non-identifiable data etc.
- Network security measures: including site firewalls, antivirus software, and separate secure network protected hosting etc.
- System Management: the System shall be developed by the BCTU Programming Team and will be implemented and maintained by the BCTU Programming Team.
- System Design: the system shall comprise of a database and a data entry application with firewalls, restricted access, encryption and role based security controls.
- Operational Processes: the data will be processed and stored within the trial centre (University of Birmingham).
- Data processing: Statisticians will only have access to anonymised data.
- System Audit: The System shall benefit from the following internal/external audit arrangements:
 - o Internal audit of the system
 - An annual IT risk assessment
- Data Protection Registration: The University of Birmingham has Data Protection Registration to cover the purposes of analysis and for the classes of data requested. The University's Data Protection Registration number is Z6195856.

11.6. **Archiving**

All records created by following trial procedures, and all documents listed in guidance relating to the conduct of the trial, must be retained and archived including electronic documents, where used. No documents should be destroyed without prior approval from the VITDALIZE UK Trial Office.

It is the responsibility of the PI to ensure all essential trial documentation and source documents (e.g. signed ICFs, ISFs, Pharmacy Files, patients' hospital notes, copies of CRFs etc.) at their site are securely retained for at least 25 years.

The TMF will be stored at BCTU for at least 3 years after the end of the trial. Long-term offsite data archiving facilities will be considered for storage after this time; data will be stored securely and confidentially for at least 25 years. BCTU has standard processes for both hard copy and computer database legacy archiving.

12. QUALITY CONTROL AND QUALITY ASSURANCE

12.1. Site Set-up and Initiation

The CI is required to sign a Clinical Trials Task Delegation Log, which documents the agreements between the CI, BCTU and the NCC. In addition, all local PIs will be asked to sign the necessary agreements including a Site Signature and Delegation Log and supply a current signed CV and GCP certificate to BCTU. All members of the site research team are required to sign the Site Signature and Delegation Log, which details which tasks have been delegated to them by the PI.

Prior to commencing recruitment, each recruiting site will undergo a process of initiation, either a meeting or a teleconference, at which key members of the site research team are required to attend, covering aspects of the trial design, protocol procedures, adverse event reporting, collection and reporting of data and record keeping. Sites will be provided with an ISF and a Pharmacy File containing essential documentation, instructions, and other documentation required for the conduct of the trial. The VITDALIZE UK Trial Office must be informed immediately of any change in the site research team.

12.2. **Monitoring**

The monitoring requirements for this trial have been developed following trial specific risk assessment by BCTU.

12.3. Central Monitoring

The VITDALIZE UK Trial Office will be in regular contact with the site research team to check on progress and address any queries that they may have. The VITDALIZE UK Trial Office will check incoming ICFs, CRFs and the eCRF for compliance with the protocol, data consistency, missing data, and timing. In addition, the Sponsor will review the data held on the eCRF and produce data queries approximately every 6 months. These queries will be sent to the VITDALIZE UK Trial Office who will in turn, distribute them to the applicable participating sites. Sites will be requested to send in copies of signed ICFs and other documentation for in-house review for all patients who have provided explicit consent for this to take place. This will be detailed in the Monitoring Plan.

12.4. **Onsite Monitoring**

Onsite monitoring will be carried out as required following a trial-specific risk assessment and as documented in the Monitoring Plan. Any monitoring activities will be reported to the research team at site and any issues noted will be followed up to resolution. Additional onsite monitoring visits may be triggered, for example by poor CRF return, poor data quality, low SAE reporting rates, excessive number of patient withdrawals or deviations. If a monitoring visit is required, the VITDALIZE UK Trial Office will contact the site to arrange a date for the proposed visit and will provide the site with written confirmation. The research team at site will allow designated BCTU staff access to source documents as requested. Appropriate staff at BCTU and the Sponsor will conduct any onsite monitoring in the UK.

12.5. Audit and Inspection

The PI will permit trial-related monitoring, audits, ethical review, and regulatory inspection(s) at their site, providing direct access to source data/documents. The PI will comply with these visits and any required follow up. Sites are also requested to notify BCTU of any relevant inspections.

12.6. Notification of Serious Breaches

In accordance with Regulation 29A of the Medicines for Human Use (Clinical Trials) Regulations 2004 and its amendments, the VITDALIZE UK Trial Office will notify the UK licensing authority on behalf of the Sponsor in writing of any serious breach of the conditions and principles of GCP in connection with that trial or the protocol relating to that trial, within 7 days of becoming aware of that breach.

For the purposes of this regulation, a "serious breach" is a breach that is likely to affect:

- The safety or physical or mental integrity of the subjects of the trial
- The scientific value of the trial

Sites are therefore requested to notify the VITDALIZE UK Trial Office of any suspected trial-related serious breach of GCP and/or the trial protocol. Where the VITDALIZE UK Trial Office is investigating whether or not a serious breach has occurred sites are also requested to cooperate with the VITDALIZE UK Trial Office in providing sufficient information to report the breach to the MHRA where required and in undertaking any corrective and/or preventive action. Sites may be suspended from further recruitment in the event of serious and persistent non-compliance with the protocol and/or GCP, and/or poor recruitment. Any major problems identified during monitoring may be reported to the CI, Sponsor, Trial Management Group (TMG), Trial Steering Committee (TSC), the REC and the relevant

regulatory bodies. This includes reporting serious breaches of GCP and/or the trial protocol to the REC and MHRA. A copy is sent to the University of Birmingham Clinical Research Compliance Team and Medical University of Graz Governance Team at the time of reporting to the REC and/or relevant regulatory bodies.

13. END OF TRIAL DEFINITION

The end of trial will be 6 months after the last data capture¹. This will allow sufficient time for the completion of protocol procedures, data collection and data input. The VITDALIZE UK Trial Office will notify the MHRA and REC that the trial has ended within 90 days of the end of trial. Where the trial has terminated early, the VITDALIZE UK Trial Office will inform the MHRA and REC within 15 days of the end of trial. The VITDALIZE UK Trial Office will provide them with a summary of the clinical trial report within 12 months of the end of trial. A copy of the end of trial notification as well as the summary report will also be sent to the Sponsor.

¹ 'Last data capture' is defined as being the last data capture for the whole trial (all participating countries).

14. STATISTICAL CONSIDERATIONS

14.1. Sample Size

The sample size for the multinational trial is based on the primary endpoint 28-day mortality. In the VITdAL-ICU trial, in the pre-defined subgroup with severe VDD, 28-day mortality rates of 36% (37/102) in the placebo group and 20% (20/98) in the vitamin D group were observed (51). The VITDALIZE trial has been designed to be powered to detect a smaller, but clinically relevant absolute mortality difference of 5% with a power of 80% or a 6% difference with 90% power with an assumed baseline mortality rate of 25% (close to the lower limit of the 95% CI of the 36% mortality observed in VITdAL-ICU). This corresponds to a clinically important relative risk reduction of between 20% and 24%. Using a fixed sample size design and a 2-sided log-rank test for equality of survival curves with a 2-sided alpha level of 5%, a sample size of over 1000 patients per group will be needed (total sample size of approximately 2200). The table below shows this, and varies the baseline event rate from 25% to 30% to illustrate that our assumptions are robust to modest variations in our assumptions.

Placebo 28-day all-cause mortality	25%		30%	
	80% power	90% power	80% power	90% power
VitD 28-day all-cause mortality	20%	19%	25%	24%
Hazard ratio	0.78	0.73	0.81	0.77
N = (per group)	1093	1002	1248	1149
Total number of events required	486	434	686	620
N = (total)	2186	2004	2496	2298

Accounting for a drop-out rate of approximately 10% yields a total sample size of N=2400 patients with the UK contributing 25% of the sample size with 600 patients. Loss to follow up in critical care trials for 28-day mortality is low and is approximately 3% in previously published critical care trials (51, 56, 57) so this 10% estimate of loss to follow up is also conservative.

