The overall aim for the UK arm of VITDALIZE is to conduct a large international randomised controlled trial to determine if treatment with a high dose of vitamin D improves patient outcomes and is cost-effective, in comparison to placebo in severely vitamin D deficient (VDD) critically ill patients admitted to an intensive care unit (ICU).

Objectives

Primary objective

To determine whether treating severe VDD with high dose oral vitamin D3 replacement in adult critically ill patients decreases 28-day mortality.

Secondary objectives

To determine whether treating severe VDD with high dose oral vitamin D3 replacement in adult critically ill patients:

- Reduces organ dysfunction
- · Reduces hospital and ICU length of stay and mortality
- Improves long-term survival
- · Reduces readmission to hospital
- · Improves activities of daily living

In the **UK** arm additionally:

- Improves health-related quality of life at 90 days and 1 year
- Reduces disability at 90 days and 1 year
- Reduces health care utilisation to 1 year
- · Is cost-effective in the NHS setting

Exploratory objectives

 To assess the feasibility of patient quality of life and disability at day 0 using the proxy EQ-5D-5L and proxy WHODAS 2.0 questionnaires

Trial Design

This is the UK arm of a large international randomised double-blind placebo-controlled trial. Patients will be randomised to the intervention or control arm in a 1:1 ratio stratified by centre and sex via a web-based central randomisation system managed by the Institute for Medical Informatics, Statistics and Documentation, Medical University of Graz.

Participant Population and Sample Size

The target population is adult critically ill patients (≥18 years) admitted to ICU with severe VDD (25(OH)D ≤12ng/ml (30nmol/L)). Total sample size of international trial n=2,400 of whom approximately 800 will be recruited in the UK.

Eligibility Criteria

Inclusion Criteria

To be eligible to participate in the VITDALIZE UK Trial, patients must meet all the following inclusion criteria:

- 1. Patients ≥18 years
- 2. Anticipated ICU stay ≥48 hours
- 3. Admission to ICU ≤72 hours before screening for VDD
- 4. Severe VDD (25(OH)D ≤12ng/ml (30nmol/L)) after ICU admission

Exclusion Criteria

If any of the following apply, the patient is not eligible to be randomised into the VITDALIZE UK Trial:

- 1. Severe gastrointestinal dysfunction (>400ml nasogastric tube residual volume) /unable to receive trial medication

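### Section 14.1 calls the design robust to a 30% placebo rate, but its own table needs 2496 patients for the 5-point difference against 2400 planned (power about 74–79%); the UK share also conflicts with the Trial Summary

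*Protocol*

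**What the plan says.** Section 14.1 sizes the trial with a "2-sided log-rank test for equality of survival curves with a 2-sided alpha level of 5" per cent. The stated targets are an "absolute mortality difference of 5% with a power of 80% or a 6% difference with 90% power", "with an assumed baseline mortality rate of 25" per cent. The section describes this as a relative reduction of 20% to 24%.

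The table then has two columns at 25% placebo mortality (25% vs 20%, 25% vs 19%) and two at 30% (30% vs 25%, 30% vs 24%). The totals before drop-out are 2186, 2004, 2496 and 2298. The sentence introducing it says that it "varies the baseline event rate from 25% to 30% to illustrate that our assumptions are robust to modest variations in our assumptions".

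The section closes the calculation with "Accounting for a drop-out rate of approximately 10% yields a total sample size of N=2400 patients with the UK contributing 25" per cent (600 patients). It adds that loss in comparable trials is about 3%, so that 10% is conservative.

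The Trial Summary, under Participant Population and Sample Size, says: "Total sample size of international trial n=2,400 of whom approximately 800 will be recruited in the UK".

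**The concern.** The 30% columns are offered as evidence that the sample size survives a higher placebo rate. One of the two asks for more patients than the trial will randomise, even before anyone is lost. It is the column that carries over the 5-point difference and the 80% target.

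What is at stake is how a null result would be read. If placebo mortality were near 30%, a reader relying on section 14.1 would assume about 80% power for a 5-point difference, and the trial would have somewhat less.

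The UK contribution is a separate matter. Two current sections of the same protocol version give different numbers.

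**Working it through.** **Inputs.** From section 14.1: two-sided alpha 5%; the mortality pairs and powers in the table; planned N=2400; loss of 10% (planning) or 3% (cited). From section 3.1: 1:1 allocation.

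**Step 1: reproduce the table.** Take 30% vs 25% at 80% power, with (1.960 + 0.842)² = 7.849.

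- Hazard ratio = ln(1 − 0.25) / ln(1 − 0.30) = 0.8066 (the table prints 0.81).
- Freedman events = 7.849 × [(1 + HR)/(1 − HR)]² = 7.849 × (1.8066/0.1934)² ≈ 685. Patients per group = 685 / 0.275 / 2 ≈ 1246.
- Schoenfeld events = 4 × 7.849 / (ln HR)² ≈ 680, or 1237 per group.
- Two proportions: n = [1.960√(2p̄q̄) + 0.842√(p₁q₁ + p₂q₂)]² / 0.05² ≈ 1251 per group.

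The table prints 686 events and 1248 per group. The other columns also reproduce. Freedman gives 1094, 1003 and 1147 per group, against 1093, 1002 and 1149 printed. The table is sound.

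**Step 2: compare with the planned total.** The requirement is 2 × 1248 = 2496, which exceeds 2400 with no loss at all. Inflated for loss, it is 2496/0.90 = 2774 (10%) or 2496/0.97 = 2574 (3%).

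**Step 3: power delivered at N=2400.** Evaluable patients are 2400 × 0.90 = 2160, 2400 × 0.97 = 2328, or 2400. Events = evaluable patients × mean event rate. Power by Freedman = Φ(√events × (1 − HR)/(1 + HR) − 1.960). By Schoenfeld it is Φ(√events × |ln HR|/2 − 1.960).

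For 30% vs 25% at 10% loss, events = 2160 × 0.275 = 594. Freedman gives Φ(24.37 × 0.1071 − 1.960) = Φ(0.65) ≈ 74.2%. Schoenfeld gives 74.5% and two proportions 74.0%.

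The ranges below run across the three methods.

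| Placebo vs vitamin D | Table's power target | 10% loss (2160) | 3% loss (2328) | No loss (2400) |
|---|---|---|---|---|
| 25% vs 20% | 80% | 79.5–80.0% | 82.4–82.8% | about 84% |
| 25% vs 19% | 90% | 92.0–92.4% | 93.8–94.1% | 94–95% |
| 30% vs 25% | 80% | 74.0–74.5% | 77.1–77.6% | 78–79% |
| 30% vs 24% | 90% | 88.2–88.6% | 90.4–90.8% | 91–92% |

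**Step 4: absolute against relative effect.** The relative reduction is 5/25 = 20% in the first column, 5/30 = 16.7% in the third and 6/30 = 20% in the fourth. The third column therefore holds the 5-point difference but has a smaller relative effect than the 20–24% the section names. The fourth holds the 20% relative reduction. For that reduction, power at 10% loss rises from about 80% at a 25% placebo rate to 88–89% at 30%.

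**Step 5: UK share.** Section 14.1: 600/2400 = 25%. Trial Summary: 800/2400 = 33%.

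**The case against.** The strongest reply is that the robustness sentence is true on the relative scale. The section states its effect as a 20–24% relative reduction as well as an absolute difference. A 20% reduction from 30% gives 24%, for which the table needs 2298, fewer than 2400. The failing column assumes a smaller relative effect than the section claims to target. This stands, and it is why the sentence needs qualifying rather than deleting.

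Second, 74% is the low end. It requires the full 10% loss, with every lost patient contributing nothing. Under a log-rank test, lost patients contribute until censoring. If losses were spread evenly over 28 days (an assumption), about 5% of events would be lost and power would be about 76–77%. This also stands, so the result is a range. But its top, with no loss at all, is still below 80%.

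Third, the prose claims 80% and 90% power only at a 25% placebo rate, and the table openly prints 2496. This is correct. A reader might infer that the protocol promises 80% power for 30% vs 25%, but it does not. The fault is in offering that column as evidence of robustness.

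Some stronger readings are tempting, and the document does not support them.

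- *The base case is short as well, because 2186/0.9 = 2429.* The section says approximately 10%, and power at 2160 evaluable patients is 79.5–80.0%. This is rounding.
- *Placebo mortality will probably exceed 25%.* The one supporting figure is 37/102 in a subgroup of the earlier trial, which section 1.2 treats as hypothesis generating. The exclusion of patients with DNAR orders or not expected to survive 48 hours pulls the other way. The document does not settle the direction.
- *The UK complier average causal effect and economic analyses use a wrong denominator.* Sections 14.3.3 and 14.4 to 14.6 state no UK denominator, so the 600/800 conflict does not reach them on paper.

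**Conclusion.** The point holds in limited form. The table is correct. The sentence built on it is not correct for a fixed 5-point difference at 30% placebo mortality, where N=2400 gives about 74% power (10% loss), 77–78% (3% loss) or 78–79% (no loss) against 80%. For a relative reduction of about 20% (30% vs 24%) the sentence nearly holds: 88–89% at 10% loss and 90–91% at 3% loss, against 90%.

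The figures assume proportional hazards, 1:1 allocation, a two-sided 5% test, and lost patients contributing no events. Three standard formulas agree to within about half a percentage point. The shortfall is modest and confined to one scenario. It is no ground for calling the trial underpowered for its stated base case.

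The UK figures conflict between two current sections. The version history records a change to the UK sample size under SA5, which suggests that section 14.1 was left behind. The international total is 2400 in both places, so the primary power is unaffected.

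**What to change.** In section 14.1:

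1. Qualify the robustness sentence. Say that at a 30% placebo rate power is maintained for a relative reduction of about 20%, but falls to about 74–79% for a fixed 5-point difference, depending on loss.
2. Add the power delivered at N=2400 for each of the four columns under 10% and 3% loss. In column order this is about 80%, 92%, 74% and 88% at 10% loss, and about 82–83%, 94%, 77–78% and 90–91% at 3% loss.
3. Reconcile the UK contribution (25%, 600 patients) with the Trial Summary (about 800, or 33%), so that one current figure appears throughout.

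The cost is text only. The design, total sample size and analysis do not change. The stated power at a 30% placebo rate becomes slightly less favourable for the 5-point difference.
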